2.3. Sample Size Calculation and Randomization

2.3.1. Sample Size Calculation

Sample size calculation is based on the primary endpoint, time to pericarditis recurrence defined as the time from randomization to the date of the first pericarditis recurrence for each subject. Time to pericarditis recurrence is assumed to follow an exponential distribution. An event of interest is defined as a subject's first adjudicated recurrence of pericarditis. The following assumptions are used in the sample size calculation using EAST 6.4.1:

- 1-sided significance level: 2.5%
- Power: 90%
- Median time to event (in weeks) in placebo: 8
- Hazard ratio (rilonacept/placebo): 0.244
- Percentage of subjects in the RI period that will not reach RW: 10%.

Given these assumptions, a total of 22 adjudicated pericarditis recurrence events is required to achieve the power. About 25 subjects per arm (a total of 50 subjects) or more will be randomized. Considering 10% of subjects in the RI period that will not reach the RW period, approximately 56 subjects will be enrolled in this study.

Subject enrollment and the pericarditis recurrence event accrual will be closely monitored during the study. The monitoring activities will be done in a blinded fashion during the RW period. If the number of subjects randomized is less than 50 and/or the time anticipated for the number of events required for the analysis of primary efficacy endpoint significantly exceeds the projected timeline, additional subjects may be enrolled and/or randomized at Kiniksa Pharmaceutical's discretion. However, at this time it is anticipated that no more than 100 subjects will be enrolled into this study.

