4. ANALYSIS SETS

4.1. Intent-to-Treat (ITT) Analysis Set

All subjects who are randomized in the RW period will be included in the Intent-to-Treat (ITT) analysis set. The primary analysis for efficacy endpoints in the RW period will be based on the ITT analysis set unless otherwise specified. Treatment comparisons for all analyses will be based on each subject's treatment assignment from randomization.

The following analysis sets are defined for the analysis of secondary endpoints:

- ITT Week 24 analysis set: All subjects randomized at least 24 weeks before data cutoff will be included. This analysis set will be used for secondary efficacy endpoints measured at week 24 in the RW period.
- ITT Week 16 analysis set: All subjects randomized at least 16 weeks before data cutoff will be included. This analysis set will be used for secondary efficacy endpoints measured at week 16 in the RW period.
- ITT Week 8 analysis set: All subjects randomized at least 8 weeks before data cutoff will be included. This analysis set will be used for secondary efficacy endpoints measured at week 8 in the RW period.

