5.2.2.3. Other Secondary Efficacy Endpoints in the RW Period and Statistical Method

All time-to-event endpoints start from the day of randomization. The same censoring rules for the primary endpoint will be applied. Missing values will not be imputed unless otherwise specified. Analysis of secondary endpoints will be based on ITT analysis unless otherwise specified.

1. Proportion of subjects who maintained Clinical Response at Week 24 of the RW period based on ITT Week 24 analysis set

The same rules and method for the first major secondary endpoint will be applied, except that 16 weeks is replaced with 24 weeks.

2. Proportion of subjects who maintained Clinical Response at Week 8 of the RW period based on based on ITT Week 8 analysis set

The same rules and method for the first major secondary endpoint will be applied, except that 16 weeks is replaced with 8 weeks.

3. Percentage of days with minimal or no pain in the first 24 weeks post randomization based on ITT Week 24 analysis set

The same rules and method for the second major secondary endpoint will be applied, except that 16 weeks is replaced with 24 weeks.

4. Percentage of days with minimal or no pain in the first 8 weeks post randomization based on ITT Week 8 analysis set

The same rules and method for the second major secondary endpoint will be applied, except that 16 weeks is replaced with 8 weeks.

5. Proportion of subjects with absent or minimal pericarditis symptoms (based on the 7-point PGIPS) at Week 24 of the RW period based on subjects who were randomized at least 24 weeks before data cutoff

The same rules and method for the third major secondary endpoint will be applied, except that 16 weeks is replaced with 24 weeks.

6. Proportion of subjects with absent or minimal pericarditis symptoms (based on the 7-point PGIPS) at Week 8 of the RW period based on subjects who were randomized at least 8 weeks before data cutoff

The same rules and method for the third major secondary endpoint will be applied, except that 16 weeks is replaced with 8 weeks.

7. Proportion of subjects without pericarditis recurrence in the first 24 weeks of the RW period

The proportion of subjects without pericarditis recurrence in the first 24 weeks of the RW period in each arm will be estimated using the KM method, as described in the

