The EQ-5D-5L is a subject reported health status utility index for adult subjects that is comprised of five questions plus a visual analog scale (VAS). The five questions ask the respondent to assess their health in terms of mobility, self-care, usual activities,

pain/discomfort, and anxiety/depression. The VAS captures the respondent's self-reported level of the health on the day of completion, captured as a numeric input from 0 ('the worst health you can imagine') to 100 ('the best health you can imagine'). Subject responses will be scored, including the handling of missing values, as specified in the EuroQol Research Foundation, EQ-5D-5L User Guide, 2019, available from <http://euroqol.org/publications/user-guides>.

Scores from the five questions will be reported individually and converted to a single index value using the value set for US. Health state index scores generally range from less than 0 (where 0 is the value of a health state equivalent to dead; negative values representing values as worse than dead) to 1 (the value of full health), with higher scores indicating higher health utility.

22. Change in subject's sleep quality assessed with the Insomnia Severity Index (ISI).

The ISI is a 7-item self-report questionnaire assessing the nature, severity, and impact of insomnia. The usual recall period is the "last 2 weeks" and the dimensions evaluated are severity of sleep onset, sleep maintenance, early morning awakening problems, sleep dissatisfaction, interference of sleep difficulties with daytime functioning, noticeability of sleep problems by others, and distress caused by the sleep difficulties. A 5-point Likert scale is used to rate each item (e.g., 0=no problem; 4=very severe problem), yielding a total score ranging from 0 to 28 (Morin et al 2011).

The ISI will be collected in subjects ≥ 18 years or older as described in the protocol.

23. Change in ISI categories. The ISI total scores are divided to 4 categories:

- 1) 0–7 = No clinically significant insomnia
- 2) 8–14 = Subthreshold insomnia
- 3) 15–21 = Clinical insomnia (moderate severity)
- 4) 22–28 = Clinical insomnia (severe)

A shift table will also be used to summarize the changes over time.

24. Cumulative number (percentage) of subjects who received sequential ORT, corticosteroid, or bailout riloncept for pericarditis period every 4 weeks cumulatively in the RW period.

The CMH test stratified by the randomization strata will be applied to this endpoint.

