25. Proportion of subjects using ORT (analgesics, NSAIDs, and/or colchicine) for pericarditis in the first 24 weeks. ORT use while waiting for at least 5 days since previous administration of study medication before receiving bailout riloncept or within 5 days prior to the assessment of pericarditis recurrence visit is excluded. The denominator of the percentages is the number of subjects in the ITT analysis set in each arm. There will be no hypothesis testing for this endpoint.

26. The endpoints below for MRI assessments will be summarized at RW baseline and week 24. P-values will not be calculated.

- Proportion of subjects with pericardial delayed hyperenhancement

- Proportion of subjects with myocardial delayed hyperenhancement
- Proportion of subjects with pericardial effusion, and effusion size

A subject will have pericardial effusion if the effusion size is rated “Small” or larger.

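### Endpoint 25 divides 24-week ORT use by the full ITT set in an event-driven period, so use is biased low in both arms; endpoint 24 has the same exposure through the ITT default

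*SAP*

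**What the plan says.** All references are to SAP v2.0.

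- **RW length.** Sections 2.1 and 2.4 make RW event-driven. Its end is announced once at least 22 adjudicated recurrences have occurred. Sites then recall subjects for the end-of-RW visit, and data cutoff follows when all have completed it.
- **Endpoint 25 (section 5.2.2.3).** This is the proportion using ORT (analgesics, NSAIDs, colchicine) in the first 24 weeks. ORT taken while waiting for bailout, or within 5 days before the recurrence assessment visit, is excluded. The divisor is explicit: "The denominator of the percentages is the number of subjects in the ITT analysis set in each arm". There is no test, no censoring rule and no Week 24 restriction.
- **Endpoint 24 (same section).** This is the cumulative number and percentage receiving ORT, corticosteroid or bailout rilonacept, every 4 weeks over RW. It states no denominator and no 24-week limit. On testing: "The CMH test stratified by the randomization strata will be applied to this endpoint".
- **Default set.** The section opens with "Analysis of secondary endpoints will be based on ITT analysis unless otherwise specified", so endpoint 24 falls to ITT.
- **Other 24-week endpoints.** Section 4.1 defines an ITT Week 24 set of subjects randomized at least 24 weeks before cutoff: "This analysis set will be used for secondary efficacy endpoints measured at week 24 in the RW period". Endpoints 1, 3 and 13 use it, and endpoint 5 states the same restriction. For endpoint 7, freedom from recurrence in the first 24 weeks, the proportion "in each arm will be estimated using the KM method".

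**The concern.** A 24-week proportion needs 24 weeks of observation or a method that allows for less. Suppose a subject is randomized 6 weeks before cutoff and has taken no ORT. That subject's status at Week 24 is unknown, but endpoint 25 puts them in the denominator and not in the numerator. Unobserved follow-up is scored as the favourable outcome. The error runs one way: the reported percentage cannot exceed what full follow-up would have shown, and it falls short whenever a subject with truncated follow-up would have gone on to use ORT.

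The general rule against imputing missing values does not help, because a used/not-used count has no missing category for someone whose RW simply ended.

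Endpoint 24 has the same weakness, and it grows at each later 4-week point as more subjects have been truncated. There it also enters a test, because the CMH comparison treats truncated subjects as known non-users.

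At stake are the reported rescue and bailout percentages and the absolute difference between arms.

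**Working it through.** **1. Inputs from section 2.3.1.** Exponential times; "1-sided significance level: 2.5"%; power 90%; "Median time to event (in weeks) in placebo: 8"; "Hazard ratio (rilonacept/placebo): 0.244"; 22 events; about 50 randomized 1:1.

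**2. Reproduce the SAP's own figure.** Schoenfeld events = 4(1.960 + 1.282)² / (ln 0.244)² = 21.1, rounded up to 22. This agrees with the SAP. Enrolment: 50 / 0.90 = 55.6, that is 56, which also agrees.

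**3. True 24-week cumulative incidence of recurrence under these inputs.**
- Placebo: 1 − 0.5^(24/8) = 0.875.
- Rilonacept: 1 − 0.125^0.244 = 0.398.
- Difference: 87.5 − 39.8 = 47.7, about 48 points.

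**4. Crude ITT percentage at Week 24.** The SAP gives neither an accrual pattern nor the lag from the 22nd event to cutoff. Both are therefore assumed: uniform accrual of 50 planned subjects, and a lag of 0, 3 or 6 weeks. RW entry stops at the 22nd event. Recurrence stands in for first ORT, corticosteroid or bailout use, so the table illustrates endpoint 24 only. Figures are averages over simulated trials.

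| Accrual | Lag | Randomized | Share with ≥24 weeks | Placebo crude | Rilonacept crude | Difference |
|---|---|---|---|---|---|---|
| 26 wk | 0 | 49 | 11% | 64% | 25% | 39 |
| 26 wk | 3 | 49 | 22% | 72% | 29% | 43 |
| 26 wk | 6 | 49 | 34% | 78% | 32% | 46 |
| 52 wk | 0 | 41 | 41% | 70% | 29% | 41 |
| 52 wk | 3 | 41 | 49% | 77% | 32% | 44 |
| 52 wk | 6 | 41 | 56% | 80% | 35% | 46 |

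Differences were taken before rounding. The share is of subjects actually randomized; with 52-week accrual the 22nd event arrives when only about 41 of the planned 50 are in RW. The crude value lies below the true value in both arms in every row.

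**5. Endpoint 25.** The SAP states no ORT rate. Purely as an assumption, take true 24-week ORT use of 20%, 50% or 80% with a constant hazard and no lag. Dividing by full ITT gives about 12%, 31% and 55% with 26-week accrual, and about 15%, 38% and 63% with 52-week accrual. These figures show direction and scale; they do not predict ORT use in this trial.

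**6. Side by side.** Endpoints 3, 7 and 25 all concern the first 24 weeks. Endpoint 3 uses the Week 24 set, endpoint 7 uses Kaplan-Meier, and endpoint 25 uses neither. The SAP gives no reason for the difference.

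**The case against.** Several points on the other side stand.

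- **No confirmatory claim is touched.** Endpoint 25 is descriptive. Endpoint 24 lies outside the hierarchy in section 3.3, which covers the primary and three major secondary endpoints.
- **The bias does not favour rilonacept.** Closure of RW is unrelated to arm, so truncation shrinks the contrast. A null simulation of the crude Week 24 comparison, unstratified, rejected 2.5 to 3.0% of the time at a one-sided nominal 2.5%. A reader might infer from the CMH test that false positives are inflated; that is not supported to any material degree.
- **The two endpoints must be kept apart.** A reader might take the quoted denominator as covering bailout through Week 24. It belongs to endpoint 25, which counts ORT only. Bailout and corticosteroid are in endpoint 24, where ITT applies by default and no 24-week limit is set.
- **It cannot be said that most subjects will lack 24 weeks.** That is tempting, but it depends on accrual and on the lag to cutoff, neither of which the SAP gives. With 52-week accrual the share reaching 24 weeks is 41% with no lag and 56% with a 6-week lag. With no lag and slower accrual of 65 or 78 weeks, it is 52% or 58%.
- **Recurrence is a poor proxy for endpoint 25.** Its exclusions remove much of the ORT given at the onset of a recurrence.

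None of this removes the downward bias in the percentages or the inconsistency with the other 24-week endpoints.

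**Conclusion.** The point holds for endpoint 25 as written: its denominator rule gives a percentage biased low in both arms, and it departs without explanation from endpoints 1, 3, 5, 7 and 13. Endpoint 24 has the same exposure through the ITT default, increasingly so at later time points, and there it attenuates a tested but non-confirmatory contrast.

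The direction follows from the text alone. The size rests on assumptions. For endpoint 24, taking recurrence as first use and uniform accrual over 26 to 52 weeks, the Week 24 arm difference reads about 39 to 41 points against 48 if cutoff falls at the 22nd event. With a 3 to 6 week lag it reads about 43 to 46, a loss of roughly 2 to 5 points. For endpoint 25 no reliable size can be given, because the SAP states no ORT rate. This is worth correcting in the wording, but the primary and major secondary conclusions do not depend on it.

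**What to change.** **Endpoint 25.** Report 1 minus Kaplan-Meier at Week 24 for time to first qualifying ORT use, by arm, censored at the end of each subject's RW follow-up. Keep its stated ORT exclusion. At minimum, replace the full ITT denominator with the existing ITT Week 24 set. Kaplan-Meier is preferable because that set could be small: with no lag, about 5 subjects (11% of 49) under 26-week accrual and about 17 (41% of 41) under 52-week accrual.

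**Endpoint 24.** State the denominator. Either report 1 minus Kaplan-Meier at each 4-week point, or restrict each point's denominator and CMH test to subjects randomized at least that many weeks before cutoff. Do not carry over endpoint 25's ORT exclusion, which endpoint 24's text does not contain. Replacing the CMH tests with a single log-rank test is possible, but the defect does not require it.

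**Cost.** A few lines of SAP wording; the Kaplan-Meier program for the primary endpoint can be reused. The price is wider intervals at late weeks, where few subjects remain at risk.

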5.2.3. Secondary Endpoints in RI and LTE Period

These include efficacy endpoints in the RI period and the LTE. Since there is no control arm in these 2 periods, only descriptive statistics will be provided. Summary statistics will be generated following the methodologies stated in Section 3.1 using RIS or LTES analysis sets. All time-to-event endpoints start from the first day of receiving riloncept in that period. Unless specified otherwise, the denominator of a response rate or percentage will be the total number of subjects treated in that period.

5.2.3.1. Secondary Endpoints in the RI Period

The following efficacy endpoints will be included for the RI period. Unless specified otherwise, change means change from RI baseline to RI week 12, and the denominator for a proportion is the total number of subjects who were treated in the RI period.

1. Time to pain response, defined as number of days from first dose to the first day a subject’s daily pain NRS is ≤ 2 of the 3 days over which, the rolling average daily pain NRS is ≤ 2 . Subjects with baseline NRS ≤ 2 will be excluded from the analysis. If one or more daily NRS score is missing, rolling average will be considered not meeting the response criteria.
2. Time to CRP normalization (≤ 0.5 mg/dL)

Time to CRP normalization will be censored at treatment discontinuation, taking prohibited medication, or week 12, whichever occurs first. Subjects with baseline CRP ≤ 0.5 mg/dL will be excluded from the analysis.

3. Time to riloncept monotherapy

Time to riloncept monotherapy is defined as number of weeks from first dose to the first day of achieving monotherapy. Subjects without background therapies at RI baseline will be excluded from the analysis.

4. Time to treatment response defined as time from first dose to the first day of pain response (defined in endpoint 1 above), and CRP ≤ 0.5 mg/dL within 7 days before or after pain response. Treatment response day will be the day of pain response, whether pain response occurs before or after CRP ≤ 0.5 mg/dL.
5. Proportion of subjects achieving clinical response at RI week 12 based on RIS analysis set

Subjects who stopped background SOC pericarditis therapy on or before week 10, as well as who achieve CRP ≤ 0.5 mg/dL and weekly average of daily pericarditis pain score ≤ 2.0 on the 11-point NRS within the 7 days prior to and including the day of randomization on RI Week 12/Randomization are responders.

Additional analysis will be done base done the completers who finished the 12-weeks of RI treatment.

6. Number (percentage) of subjects with normalization of CRP (≤ 0.5 mg/dL) at RI Week 12. Subjects with baseline CRP > 0.5 mg/dL in the RI analysis set will be used in the analysis.
7. Change from baseline in pericarditis weekly pain score at RI Week 12 and over time.
8. Change from baseline in CRP level at RI Week 12 and over time.
9. Proportion of subjects with resolution of echocardiographic and ECG abnormalities (yes/no) at RI Week 12.
10. Percentage of days with no or minimal pain (NRS ≤ 2) while on treatment. The denominator is the number of days on treatment, calculated as [min(date of last dose of study drug in RI period + 6, last date on study, end of RI period) – date of first dose in RI period) + 1].
11. Proportion of subjects with absent or minimal pericarditis symptoms based on PGIPS over time at baseline, week 6, and week 12.
12. Proportion of subjects with absent or minimal pericarditis activity based on the PGA-PA over time at baseline, week 6, and week 12.
13. Change in the SF-36 8 domain scores, as well as the physical and mental scores.
14. Change in the SF-6D 6 domain scores and the utility index.
15. Change in the EQ-5D-5L individual scores and index value.
16. Change in the subject's sleep quality assessed with the ISI (see Section 5.2.2.3).
17. Change in ISI categories.
18. Number (percentage) of subjects who were off background pericarditis medication on or before weeks 4, 8, 10, and 12

The RI Analysis Set will be used for the summary. At each timepoint, the numerator only includes subjects who have reached monotherapy on or before the timepoint and remain on monotherapy until the end of the RI period.

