11. CHANGES FROM ANALYSES PLANNED IN THE PROTOCOL

11.1. Changes from Protocol

Analysis in the SAP	Analysis planed in the protocol	Reason
Section 5.2.2.3 Changes in SF-6D utility index score.	Section 7.2.2 Change in the SF-6D 6 domain scores and the utility index.	The 6 domains were not generated for analysis by the Optum software. They were used to calculate the utility index score only.
Section 5.2.3.1 Time to pain response, defined as number of days from fist dose to the first day a subject's daily pain NRS is ≤ 2 of the 3 days over which, the rolling average daily pain NRS is ≤ 2 .	Section 7.3.1 Time to pain response defined as a rolling average of NRS score of 2 or less on three consecutive days.	A score of 3 or higher on the first day of the rolling average should not qualify pain response.
Section 5.2.3.1 Time to treatment response defined as time from first dose to the first day of pain response, and CRP ≤ 0.5 within 7 days before or after pain response. Treatment response day will be the first day that the above criterion is met. If pain response occurs before CRP ≤ 0.5 , each 3-day rolling average of NRS should be ≤ 2.0 from the day of pain response to the day of CRP ≤ 0.5 . The response day will be the day of pain response. If CRP ≤ 0.5 occurs before pain response, the response day will also be the day of pain response.	Section 7.3.1 Time to clinical response (monotherapy + NRS ≤ 2 + CRP ≤ 0.5 mg/dL)	Subjects were enrolled with a qualifying episode and on background therapy. The endpoint of interest is to evaluate how soon subjects will reach response in both pain and CRP after initiating riloncept while on background therapy.

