Pericarditis Concomitant medication tapering					X	X	X	X	X	
Full Physical Examination ^c	X									
Abbreviated Physical Examination ^d		X								X
Body weight and height		X								X
12-Lead ECG		X								X
Echo ^e		X ^e								X ^e
MRI (substudy only)		X								
Pericardial pain (11-point NRS)	X ^f									DAILY ^g

Statistical Analysis Plan

Kiniksa Pharmaceuticals, Ltd.
Study KPL-914-C002

Trial Period	SCREENING ^a	RUN-IN (12 weeks) ^m								
		ENROLLMENT			RANDOMIZATION ^{-q}					
Visit Name	Screening Visit	RI Baseline	RI Day 2	RI Day 4	RI Week 1	RI Week 2	RI Week 4	RI Week 6	RI Week 10	RI Week 12/ RW Baseline
Visit Window ^b (days)	(-28)	NA	NA	+/- 1	+/- 2	+/- 2	+/- 2	+/- 2	+/- 2	+/- 3
Visit Type	Clinic	Clinic	Clinic	TC/RN	TC/RN	TC/RN	TC/RN	Clinic	TC	Clinic
EQ-5D		X								X
SF-36		X								X
ISI		X								X
PGIPS		X						X		X
PGA-PA		X						X		X
Hematology, Chemistry Labs (Central)		X						X		X
Lipid Panel (Central) ^h		X								X
CRP (Local)	X ^f									X
CRP (Central)	(X)	X		X	X	X	X	X		X
Hematology, Chemistry, IGRA ^t , hepatitis serology, HIV (Local)	X									
Chest X-Ray	X									
Urine Pregnancy (Local or Central) ^j	X	X								
Urinalysis (Central)		X								
PK (Central) ^s			X ⁱ		X	X	X			
ADA (Central) ^s		X				X		X		
Biomarkers (Central)		X			X		X			
Pharmacogenomics Informed Consent ^k		X								
Pharmacogenomics Sampling (Central) ^k							X			
IWRS Subject Status Update	X	X								X
IWRS Weight Input (pediatric only)		X								X

Statistical Analysis Plan

Kiniksa Pharmaceuticals, Ltd.
Study KPL-914-C002

Trial Period	SCREENING ^a	RUN-IN (12 weeks) ^m								
		ENROLLMENT								RANDOMIZATION ^{-q}
Visit Name	Screening Visit	RI Baseline	RI Day 2	RI Day 4	RI Week 1	RI Week 2	RI Week 4	RI Week 6	RI Week 10	RI Week 12/ RW Baseline
Visit Window ^b (days)	(-28)	NA	NA	+/- 1	+/- 2	+/- 2	+/- 2	+/- 2	+/- 2	+/- 3
Visit Type	Clinic	Clinic	Clinic	TC/RN	TC/RN	TC/RN	TC/RN	Clinic	TC	Clinic
IWRS Drug Dispensing		X		X				X		X
In Clinic Study Drug Administration ^o		X ⁿ						X		X
Outpatient Study Drug Administration ^o					WEEKLY					
Study Drug Compliance Review		X			X	X	X	X	X	X
Clinical Response Evaluation										X ^p
Adverse Event Reporting ^l	X	X		X	X	X	X	X	X	X

a The screening and enrollment visit can be combined.

b Scheduling of visits within visit windows requires cautious planning to ensure there is no interruption to subject evaluation and study drug treatment.

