Section 5.2.3.1 endpoint #1 time to pain response	Add "If one or more daily NRS score is missing, rolling average will be considered not meeting the response criteria."	To clarify pain response criteria.

Analysis in the draft SAP submitted to FDA on 03APR2020	Analysis in the final signed off version 1.0	Reason

Section 5.2.3.1 endpoint #4 Time to treatment response defined as time from first dose to the first day of pain response, and CRP ≤ 0.5 within 7 days before or after pain response. Treatment response day will be the first day that the above criterion is met. If pain response occurs before CRP ≤ 0.5, each 3-day rolling average of NRS should be ≤ 2.0 from the day of pain response to the day of CRP ≤ 0.5. The response day will be the day of pain response. If CRP ≤ 0.5 occurs before pain response, the response day will also be the day of pain response.
	
Time to treatment response defined as time from first dose to the first day of pain response (defined in endpoint 1 above), and CRP ≤ 0.5 mg/dL within 7 days before or after pain response. Treatment response day will be the day of pain response, whether pain response occurs before or after CRP ≤ 0.5 mg/dL.
	
Simplify definition and not requiring all 3-day rolling averages ≤ 2 before CRP ≤ 0.5

	
Add the following analysis to Section 5.2.3.1 endpoint #5 proportion of subjects achieving clinical response at RI week 12: Additional analysis will be done base done the completers who finished the 12-weeks of RI treatment
	
Add analysis for different analysis population

	
Add a new Section 11.2 for impact of COVID-19 pandemic
	
To evaluate the COVID-19 pandemic impact on study

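### Run-in treatment response is tied to the single first pain-response day, so a subject whose CRP normalizes more than 7 days later can never count as a responder

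*SAP*

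**What the plan says.** SAP v2.0, Section 5.2.3.1:

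- Endpoint 1 begins "Time to pain response, defined as number of days from first dose to the first day" on which the daily pain NRS is ≤2 within three days whose rolling average is ≤2. It yields one date per subject.
- Endpoint 4 (time to treatment response) is the "time from first dose to the first day of pain response (defined in endpoint 1 above"), with CRP ≤0.5 mg/dL "within 7 days before or after pain response. Treatment response day will be the day of pain response". It makes no provision for a CRP that normalizes later and states no censoring rule.
- Endpoint 2 (time to CRP normalization) does state one: treatment discontinuation, prohibited medication or Week 12, whichever is first.

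Section 11.1 of v2.0, in the column describing the SAP's own analysis and citing Section 5.2.3.1, says instead: "Treatment response day will be the first day that the above criterion is met". It also requires every rolling average to stay ≤2.0 between pain response and CRP normalization. It gives the purpose as to "evaluate how soon subjects will reach response in both pain and CRP" after starting rilonacept on background therapy.

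The list of changes to the SAP gives this reason for the v2.0 wording of endpoint 4: "Simplify definition and not requiring all 3-day rolling averages" at or below 2 before CRP normalizes. CRP timing is not mentioned.

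Table 4 (Section 13.1) schedules central CRP in the run-in at baseline, Day 4 and Weeks 1, 2, 4, 6 and 12, with none at Day 2 or Week 10.

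**The concern.** A measure of how soon subjects reach response in both pain and CRP should count a subject once both have been reached. Endpoint 4 asks something narrower: was CRP normal close to the day pain first resolved? If pain settles quickly and CRP follows more than a week later, the answer is no, and nothing later can change it. Such a subject can succeed on endpoint 1, on endpoint 2 and on endpoint 5 (clinical response at Week 12) and still be reported as never having had a treatment response.

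At stake is a response curve that is too low and a time summary that depends partly on the order in which pain and CRP resolve. Because Sections 5.2.3.1 and 11.1 differ, two programmers could also derive different responders.

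**Working it through.** The SAP states no figure for this endpoint, so there is none to reproduce.

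**1. Schedule.** Counting days from first dose, with Day 4 as day 3, central CRP falls on days 0, 3, 7, 14, 28, 42 and 84. The gaps are 3, 4, 7, 14, 14 and 42 days.

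**2. One subject, two pain-response days.** CRP is raised on day 7 and normal from day 14 on.

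| First pain-response day | Day-7 CRP | Day-14 CRP | Result in Section 5.2.3.1 |
|---|---|---|---|
| 3 | in window (7 − 3 = 4), raised | 14 − 3 = 11 > 7, outside | never a responder |
| 8 | in window (8 − 7 = 1), raised | 14 − 8 = 6 ≤ 7, inside, normal | responder on day 8 |

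This step needs no distributional assumption.

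**3. Coverage of the ±7-day window.** The Week 6 sample reaches day 42 + 7 = 49 and the Week 12 sample reaches back to day 84 − 7 = 77. Each nominal pain-response day from 1 to 49 has at least one scheduled CRP in its window. Days 50–76 have none (76 − 50 + 1 = 27 days).

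**4. Share lost, under assumptions.** The SAP gives no distribution for either time. Assumed: exponential times, t = −ln(1 − U) × median / ln 2; medians 3, 5, 7, 14 and 21 days for each; correlation 0 or 0.6; CRP stays normal once normal; 300,000 subjects per cell. Pain response p is rounded up to a whole day; c is the CRP normalization time. A subject counts if some scheduled day s has c ≤ s and |s − p| ≤ 7. The denominator is subjects with p ≤ 84 and c ≤ 84. The figure in brackets is the loss if CRP were measured daily, which isolates the anchor and its window (lost if c > p + 7).

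| Median pain / CRP (days) | Correlation 0 | Correlation 0.6 |
|---|---|---|
| 7 / 3 | 11.2% (5.2%) | 4.7% (0.9%) |
| 3 / 3 | 15.7% (8.7%) | 11.0% (3.8%) |
| 7 / 7 | 34.2% (23.8%) | 27.9% (15.2%) |
| 21 / 3 | 17.5% (2.3%) | 13.0% (0.1%) |
| 21 / 21 | 57.0% (37.6%) | 50.7% (30.7%) |
| 3 / 21 | 73.4% (66.1%) | 76.3% (69.4%) |

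Hand check of the bracketed figure at correlation 0: P(c > p + 7) = 2^(−7/m_c) × m_c/(m_c + m_p), where m_c and m_p are the CRP and pain medians. For 7 / 7 this is 0.5 × 0.5 = 25%, close to 23.8%; the simulation also rounds p up and conditions on both times being ≤84 days.

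Over all 50 cells the loss runs from 4.7% to 76.3%. The schedule adds 3.8 to 20.8 percentage points to the daily-CRP loss. The anchor and window account for more than half the loss in 32 of the 50 cells. In the other 18 the schedule does at least as much; these have CRP normalization fast relative to pain response, or the two correlated with similar short medians.

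**5. The day 50–76 gap.** At correlation 0, the share of the denominator with pain response on those days is 0.7% at a pain median of 7 days, 6.6% at 14 days and 12.5% at 21 days.

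**The case against.** **Is sparse CRP sampling to blame?** A reader might infer so from the schedule. The documents do not support it as the main explanation. Days 1–49 all have a scheduled CRP in the window, and the subject in step 2 is lost in the densest part of the schedule. Sampling is a contributor, and the larger one only in some scenarios.

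**Does the calendar gap show that about a third of subjects are lost?** No. The 27 days are days, not subjects. Few subjects fall there unless pain response is slow.

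**Does Section 11.1 cure the problem?** It can be read as allowing a later qualifying day, and with the joint criterion re-evaluated on later days the simulation loses nobody, provided pain response persists. But that entry also keeps the 7-day window and dates response to the pain-response day, and Section 5.2.3.1 has dropped its first-day sentence. It shows a conflict to settle, not a rescue. It is not superseded text, since its column describes the current SAP analysis.

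**Is a 7-day pairing of pain and CRP the SAP's own convention?** Yes: it appears in the recurrence, bailout and enrollment criteria. There it confirms that an episode is active. It does not justify fixing the pair at the first pain-response day in a time-to-response measure.

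**Is the information lost from the report?** Largely not. Endpoints 1, 2 and 5 report pain, CRP and Week 12 clinical response. This stands and limits the severity.

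**Conclusion.** The point holds as a defect of definition. Read as written, Section 5.2.3.1 permanently excludes a subject whose first normal sampled CRP comes more than 7 days after first pain response, and it can reject a subject because pain resolved sooner. That conflicts with the purpose given in Section 11.1, whose definition also differs.

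The size is unknown. The range of about 5% to 76% rests on assumed exponential times, the chosen medians and correlations, persistent CRP normalization and nominal visit days. It does not support saying that many subjects will be lost.

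Nor does the point reach the trial's conclusions. Section 5.2.3 makes run-in endpoints descriptive with no control arm, and the endpoint is outside the testing procedure in Section 3.3. Severity is minor.

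**What to change.** Define treatment response as the first day on which both criteria hold, without confining CRP to 7 days around the first pain-response day:

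- If the latest CRP at the pain-response day is ≤0.5 mg/dL, response is dated to the pain-response day.
- Otherwise it is dated to the first later CRP ≤0.5 mg/dL at which the current 3-day rolling NRS is still ≤2.

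In step 2, both versions of the subject would then respond on day 14, if pain control holds. A subject with pain response on days 50–76 is also classifiable, from the Week 6 CRP or otherwise at Week 12.

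Censor as in endpoint 2: treatment discontinuation, prohibited medication or Week 12, whichever is first, with a response at the Week 12 visit counted as an event. State whether local and unscheduled CRP values count. Replace the Section 11.1 entry with the same wording.

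Cost: SAP text and one reprogrammed date. The reported median may lengthen, and some response dates will fall on CRP visit days. For late pain response the latest CRP may be several weeks old (up to 83 − 42 = 41 days on the nominal schedule), which a table footnote should say.
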